12.2.5 Data Transformations

No transformations of data are planned.

12.2.6 Subject Disposition and Characteristics

The number of subjects randomized to each treatment arm will be tabulated and a flow diagram describing the disposition of subjects will be constructed. Demographic variables will include age (continuous and by age category [categorized by decade of life]), sex, race, ethnicity, height, and weight. Baseline disease characteristics will include reason for surgery and related co-morbidities. All continuous endpoints will be summarized using descriptive statistics, that will include the number of subjects (n), mean, standard deviation, median, minimum, and maximum. All categorical endpoints will be summarized using frequencies and percentages.

12.2.7 Subject Compliance

Because the study device will be applied by the study investigator during a single surgery, subject compliance with completing the efficacy evaluation is not an issue and will not be reported. Subject compliance with completing the follow-up visit will be reported.

12.2.8 Protocol Deviations

Eligibility criteria that were not met will be listed along with whether or not an exception was granted. Important protocol deviations will be summarized by treatment group. Important protocol deviations are defined as:

- Any unauthorized protocol deviations that result in a significant added risk to the study subject;
- Non-adherence to eligibility criteria without prior Sponsor approval;
- Non-adherence to good clinical practices, FDA regulations, and/or ICH guidelines (e.g., failure to obtain proper informed consent or failure to report SAEs);
- A high frequency of unauthorized non-adherence to study procedures or schedules that do not involve eligibility;
- Development of withdrawal criteria during the study without corresponding subject withdrawal;
- Receipt of a prohibited concomitant medication by a subject; and
- Protocol deviations will be summarized in tables produced by the Medical Monitor or Clinical Research Associate.

12.3 Analytic Methods

12.3.1 Analysis of Primary and Secondary Efficacy Endpoints

12.3.1.1 Analysis Population

Efficacy analyses will be conducted on the TTH Population, defined as all subjects who were randomized, received study intervention, and had a TTH assessment recorded regardless of whether the measurement was censored. Lead-in subjects are *not* part of the TTH Population.

12.3.1.2 Methods of Analysis

The primary efficacy endpoint is the difference in the probability of TTH within 6 minutes comparing HEMOBLAST™ to G+T. The lower bound of the 95% confidence interval for the difference in binomial probabilities will be used to assess comparable efficacy. The primary efficacy analysis will be conducted on data from the first identified bleeding site for each subject. The estimated difference in the probability of TTH at 6 minutes between treatment arms will be adjusted for surgical indication by weighting the stratum-specific differences in observed proportions using Cochran-Mantel-Haenszel weighting.¹⁸ The trial seeks to establish comparable efficacy based upon a non-inferiority margin of 10% for the difference in the probability of TTH within 6 minutes comparing HEMOBLAST™ to G+T (HEMOBLAST™–G+T). Letting θ denote the true difference in the probability of hemostasis at 6 minutes between HEMOBLAST™ to G+T, the trial will test the null hypothesis $H_0: \theta \leq -0.10$ vs. the alternative hypothesis $H_A: \theta > -0.10$ using a one-sided level 0.025 test. The null hypothesis of inferiority will be rejected and comparable efficacy will be established if the resulting lower bound of the 95% confidence interval for θ is greater than -0.10. Comparable efficacy will be evaluated using a group sequential testing design as described in Section 12.4 with stopping boundaries defined to ensure a maximum overall 1-sided significance level of 0.025. Following the completion of the trial, a confidence interval for the estimated difference in the probability of hemostasis at 6 minutes will be computed using the Cochran-Mantel-Haenszel estimator and asymptotic variance estimate in combination with the repeated confidence interval method.¹⁹ Estimates of the distribution of TTH over a maximum follow-up of 10 minutes will be computed based on all available assessment times (3 minutes, 6 minutes, and 10 minutes) using the Kaplan-Meier method.

Analyses of the secondary efficacy endpoints will be evaluated only once, at the end of the study, using a family-wise 2-sided significance level of 0.05. Adjustment for multiple comparisons when assessing

secondary endpoints will be performed using a fixed sequence closed testing procedure to control the family-wise type I error rate at 0.05, as described in Section 12.2.4. The difference in mean preparation time will be tested using a linear regression model with stratified adjustment for surgery type. The difference in the probability of TTH within 3 minutes will be tested using a general linear model with stratified adjustment for surgery type as described above. Wald-based 95% confidence intervals for the difference in probability of TTH will be computed.

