12.2.4 Accounting for Multiple Comparisons

The primary analysis comparing the probability of TTH within 6 minutes in subjects receiving HEMOBLAST™ to those receiving G+T will be conducted to maintain an overall 0.025 (one-sided) significance level accounting for one interim analysis and one final analysis (see Sections 12.4.1 and

12.4.2). The exclusion of a >10% difference in the probability of TTH at 6 minutes will be indicated by the lower limit of a 95% confidence interval for the adjusted difference in binomial proportions (HEMOBLAST™ – G+T). All reported inference (confidence intervals and p-values) will account for the planned interim analysis.

Adjustment for multiple comparisons when assessing secondary endpoints will be performed using a fixed sequence closed testing procedure. The experiment-wise Type I error rate will be controlled in the strong sense at a (two-sided) 5% significance level. In a fixed sequence testing procedure, the formal inferential testing can proceed to the next step only when statistical significance is declared in the current step. If the testing sequence is stopped, the remaining endpoints in the testing sequence will be considered exploratory. Furthermore, any comparisons that are not presented in the a priori specified testing procedure will also be considered exploratory. The fixed sequence testing procedure will be employed among the primary and secondary endpoints in the order presented below:

- 1) Primary endpoint: Success at achieving hemostasis within 6 minutes for the first treated bleeding site (comparable efficacy of HEMOBLAST™ relative to G+T, evaluated using a 10% non-inferiority margin);
- 2) Secondary endpoint: The difference between arms in mean preparation time, defined as the time from the opening of package to product being ready to use (measured in minutes and seconds);
- 3) Secondary endpoint: Success at achieving hemostasis within 3 minutes for the first treated bleeding site (comparable efficacy evaluated using a 10% non-inferiority margin);
- 4) Secondary endpoint: Success at achieving hemostasis within 6 minutes for the first treated bleeding site (superiority of HEMOBLAST™ relative to G+T); and
- 5) Secondary endpoint: Success at achieving hemostasis within 3 minutes for the first treated bleeding site (superiority of HEMOBLAST™ relative to G+T).

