The trial will utilize a 2:1 randomization scheme (HEMOBLAST™ : G+T). Randomization will be stratified by surgery indication and it is anticipated that accrual to each surgical indication will be roughly equal. It is envisioned that one interim analysis will be performed during the monitoring of the study, occurring after outcomes have been observed for 240 randomized and treated subjects belonging to the TTH Population (approximately 160 subjects treated with HEMOBLAST™ under 2:1 randomization), and may continue to a maximal sample size of 400 subjects (approximately 267 subjects treated with HEMOBLAST™ under 2:1 randomization). Although the above interim analysis is pre-defined, final inference for comparable efficacy will treat the futility boundary as non-binding (implying that the type I error rate for the trial will be bounded at or below .025 even if the futility boundary is crossed at the interim analysis but the trial continues on).

Under such a monitoring schedule and assuming a probability of TTH within 6 minutes of 88% in both the HEMOBLAST™ arm and the G+T arm, a maximal sample size of 400 treated subjects (267 in the HEMOBLAST™ arm and 133 in the G+T arm) will provide approximately 80.1% power to determine comparable efficacy based upon a 10% non-inferiority margin of absolute difference in the probability of TTH within 6 minutes. Of particular note, if the study were to stop in favor of comparable efficacy at the interim analysis after 60% of the maximal sample size were accrued, data would be available on approximately 160 patients in the TTH Population treated with HEMOBLAST™ plus up to an additional 50 lead-in subjects. Assuming equal accrual to each surgical indication this would provide safety data on roughly 70 subjects treated with HEMOBLAST™ for each surgery type.

Enrollment will continue in parallel with the interim analysis. Thus, if the interim analysis supports early termination of the clinical investigation, the number of subjects included may be higher than the number available at the time of the interim analysis. All available data for the analysis populations defined above will be included in the final analysis and report.

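### The 3-minute non-inferiority test uses an unadjusted 1.96 at a look chosen by the correlated group-sequential primary, so its one-sided error is about 0.027, not 0.025

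*Protocol*

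**What the plan says.** **Primary.** Protocol 12.3.1.2 tests 6-minute non-inferiority "using a one-sided level 0.025 test". Protocol 12.4.1 adds one interim analysis, "occurring after outcomes have been observed for 240 randomized and treated subjects belonging to the TTH Population", out of a maximum of 400. The efficacy bounds on the Z scale are 2.373 at the interim and 2.036 at the end (Protocol Table 9, SAP Table 3). The primary difference gets a repeated confidence interval.

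**Secondaries.** Protocol 12.3.1.2 and SAP 10.5.2 state: "Analyses of the secondary efficacy endpoints will be evaluated only once, at the end of the study", "using a family-wise 2-sided significance level of 0.05". They prescribe Wald 95% intervals for the hemostasis differences. No boundary, spending function or stage-specific level is given for any secondary.

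**Error claim.** Protocol 12.2.4 and SAP 10.10: "The experiment-wise Type I error rate will be controlled in the strong sense at a (two-sided) 5% significance level". The order is 6-minute non-inferiority, preparation time, 3-minute non-inferiority, 6-minute superiority, 3-minute superiority, and "formal inferential testing can proceed to the next step only when statistical significance is declared in the current step".

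**A sentence pointing the other way.** The same two sections, in the paragraph on the primary analysis, promise that every reported interval and p-value will allow for the interim.

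**Study end.** Enrollment continues during the interim, and all available data enter the final analysis (Protocol 12.4.1, SAP 10.7.1). The maximum can rise to 460 (Protocol 12.4.3, SAP 10.7.2).

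**The concern.** Testing a secondary once looks safe, but the sample size at which it is tested is not fixed. A high 6-minute Z at the interim ends the trial there. Maintained hemostasis at 3 minutes implies success at 6 minutes (Protocol Table 8), so the two statistics rise and fall together. Trials stopped early therefore tend to have high 3-minute Z values at that look, and 1.96 is then too low a bar.

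A fixed sequence gives strong control only if each step is a valid test under the actual stopping rule. At stake is a stated guarantee for a formal claim, 3-minute non-inferiority, which also gates both superiority claims.

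**Working it through.** **1. Reproduce the design.** Inputs from Protocol 12.4.1: "assuming a probability of TTH within 6 minutes of 88% in both the HEMOBLAST™ arm and the G+T arm", a 10-point margin, 160/80 subjects at the interim, 267/133 at the end.

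- SE at the interim = √(0.88 × 0.12 × (1/160 + 1/80)) = 0.0445; drift 0.10/0.0445 = 2.247.
- SE at the end = √(0.88 × 0.12 × (1/267 + 1/133)) = 0.0345; drift 0.10/0.0345 = 2.899.
- Correlation of the primary Z between looks = √(240/400) = 0.775.
- One-sided alpha = 1 − P(Z1 < 2.373, Z2 < 2.036) = 0.0250, as stated.
- Power is 80.0% with futility followed and 81.4% with it ignored, against the stated 80.1%.
- Chance of an efficacy stop at the interim = 1 − Φ(2.373 − 2.247) = 45%.

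**2. Error of a secondary at 1.96.** Let P1, P2 be the primary Z and S1, S2 the secondary Z at its own null, with correlation ρ at the same look:

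error = P(P1 ≥ 2.373, S1 > 1.96) + P(P1 < 2.373, P2 ≥ 2.036, S2 > 1.96).

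This takes the preparation-time gate as passed.

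**3. Correlation.** The documents give no 3-minute rate, so ρ is an assumption. For nested outcomes with equal rates in both arms, ρ = p3(1 − p6)/√(p3(1 − p3)p6(1 − p6)). With p6 = 0.88, 3-minute rates of 60%, 70% and 80% give 0.45, 0.56 and 0.74.

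**4. Results for 3-minute non-inferiority (one-sided, nominal 0.025; 2 million simulated paths per row, no overrun).**

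| ρ | 6-minute rates 88%/88% | Maximum over the true 6-minute difference |
|---|---|---|
| 0.45 | 0.0268 | 0.0268 |
| 0.56 | 0.0271 | 0.0275 |
| 0.74 | 0.0265 | 0.0292 |

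With futility followed the maxima are 0.0266, 0.0273 and 0.0291. As a cross-check, ρ was recomputed with the 3-minute rate 10 points lower on HEMOBLAST, as its null requires. Control 3-minute rates of 50% to 85% then give 0.0258 to 0.0270 at 88%/88%, and maxima of 0.0260 to 0.0312.

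**5. Ceiling.** Whatever the correlation, the error cannot exceed P(S1 > 1.96 or S2 > 1.96) = 0.0398. The highest value found, as ρ approaches 1, is about 0.039.

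**6. Overrun.** Its size is not stated. Assuming 20, 40 or 80 further subjects after an early stop, the maximum is 0.0265, 0.0262 or 0.0256 at ρ = 0.5, and 0.0311, 0.0298 or 0.0278 at ρ = 0.9.

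**7. The other secondaries.** Preparation time: 0.025 if uncorrelated with hemostasis. For 6-minute superiority at 88%, a superiority Z above 1.96 at the interim means a non-inferiority Z above 1.96 + 2.247 = 4.21, so the trial has already stopped; the error is 0.0251. For 3-minute superiority no figure was calculated that counts all its gates.

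**The case against.** **The plan already says all inference accounts for the interim.** This is the closest counter-text, and its wording is not limited to the primary. It shows intent. But it names no secondary method, the repeated interval is specified only for the 6-minute difference, and Protocol 12.3.1.2 and SAP 10.5.2 then prescribe an unadjusted 0.05 with Wald intervals. The passages conflict; the sentence does not settle the matter.

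**The stated level is two-sided 5%.** A reader might infer that the 5% total is exceeded. It is not: counting both tails after a primary success, the total stays below 0.05 because the lower tail shrinks. But a non-inferiority claim is made in one direction, so the relevant limit is 0.025.

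**The excess is small and rests on assumed inputs.** This stands. At ρ = 0.74 the peak needs a true 6-minute difference near −0.04. A reader might take 0.039 as a realistic figure, but it needs 3- and 6-minute outcomes that are in effect identical. Overrun reduces the excess further. None of this brings the error to 0.025 in the cases calculated.

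**The preparation-time gate might protect the later steps.** It is unlikely to. Protocol 3.1 says HEMOBLAST needs no preparation, mixing or heating, so this gate should nearly always pass.

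**Conclusion.** The claim of strong control is not met, as written, for 3-minute non-inferiority. Its one-sided error is about 0.027 at the planned 6-minute rates and at most about 0.027 to 0.029 for assumed correlations of 0.45 to 0.74, against 0.025. The size depends on the unstated 3-minute rate and on overrun.

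A reader might infer that all the secondaries lose control, or that study success is in doubt. The documents support neither. The primary bounds hold 0.025 exactly, 6-minute superiority at 88% and preparation time (if uncorrelated) are essentially at their level, and overall study success rests on the primary alone. This is a modest but real gap between a stated property and the prescribed method.

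**What to change.** Reconcile Protocol 12.2.4 and SAP 10.10 with Protocol 12.3.1.2 and SAP 10.5.2. Give each secondary hemostasis test its own group-sequential critical value at the look where the trial stops, recomputed for actual information, with matching intervals in place of the Wald ones. Two valid choices:

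- **A Pocock-type constant of about 2.16 at either look.** P(S1 > 2.16 or S2 > 2.16) = 0.025, so the level holds at any correlation.
- **The primary's own 2.373 and 2.036.** These also hold 0.025 at any correlation. They are stricter than needed in likely cases: maximum error about 0.014 to 0.016 for ρ of 0.45 to 0.74.

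**Cost.** Take an endpoint with 80% power at 400 subjects (drift 1.96 + 0.84 = 2.80) and 88%/88% at 6 minutes, with futility ignored. The chance that both the primary and this endpoint succeed is:

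| ρ | 1.96 | 2.16 constant | 2.373/2.036 |
|---|---|---|---|
| 0.45 | 62.8% | 57.0% | 54.6% |
| 0.74 | 69.3% | 63.6% | 61.4% |

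The constant costs between 5 and 6 points and the primary's bounds about 8. The loss is mostly in trials that stop early. The plan should state it.

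The alternative costs only wording: restrict the strong-control statement so that it does not cover the 3-minute tests after an early stop.

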12.3.2 Analysis of Safety Outcomes

12.3.2.1 Analysis Population

Safety analyses will be conducted on the Full Analysis Population, defined as all subjects who were randomized into the study and received study intervention and all lead-in subjects.

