6.4.2 Randomization and Hemostat Application

At the start of each surgical procedure, a single HEMOBLAST™ device and a single G+T device will both be prepared per the respective Instructions for Use (unless the subject is a lead-in subject; all lead-in subjects will have a single HEMOBLAST™ device prepared). The preparation time for both devices will be recorded for the TTH Population subjects.

Randomization will be performed through sequentially numbered sealed envelopes. Four-hundred subjects (TTH Population) will be randomized to receive HEMOBLAST™ or G+T in a 2:1 ratio:

- 267 subjects will be randomized to receive HEMOBLAST™; and
- 133 subjects will be randomized to receive G+T.

There will be a maximum of 50 lead-in subjects; these subjects will not be randomized. The first subject for each investigator will be treated as a lead-in subject. These subjects will receive HEMOBLAST™ and will be followed for safety only (maximum Full Analysis Population of 450); lead-in subjects will not count towards the TTH Population. Please see Section 12 below for additional detail on subject populations.

Randomization will be stratified by surgical indication and will incorporate blocking; additional details of randomization and blocking will be included in a separate Randomization Plan.

After randomization and enrollment, the assigned hemostat will be used in the investigational subject; the other hemostat will be discarded following institutional procedures.

A study-specific stopwatch will be used to track hemostat application and the times of hemostasis evaluation. The time of initial hemostat application will be considered time 0; at this time, the stopwatch will be started by the study coordinator. The stopwatch will run continuously without stopping.

Hemostasis will be evaluated by the investigator at the following time points until hemostasis has been achieved:

- 3 minutes;
- 6 minutes; and
- 10 minutes.

Reapplication of the randomized hemostat will be performed at the 3 minute and 6 minute evaluation time points, as described below.

For cardiothoracic procedures, the TBS will be identified after heparin reversal. Additionally, the TBS will not be at the site of a valve implant or at the site of a synthetic graft or patch implant.

HEMOBLAST™ will be applied according to its instructions for use.

1. Peel open the pouches to remove contents with attention to sterile procedures.
2. Remove cap using a twisting motion.

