12.3.2.2 Methods of Analysis

Summaries of the number and percent of subjects with at least one SAE will be provided. Comparisons of the proportion of subjects experiencing SAEs will be made between treatment arms. Summaries of the number of percent of AEs will be provided for each treatment arm.

Differences in mean overall blood loss, mean volume of intra-operative transfusions, mean total operative time, and mean duration of hospitalization will be estimated using linear regression models with stratified adjustment for surgery type and separated by surgery type. In all cases, the robust variance estimator will be used and a 95% Wald-based interval will be computed. Comparisons of the incidence of re-operation (total and reoperation due to bleeding) and the incidence post-surgery bleeding complications will be made using a general linear model to estimate the difference in the probability of each outcome after stratified adjustment for surgery type. Comparisons of the incidence of re-operation and the incidence post-surgery bleeding complications within each surgery type will be made using a two sample binomial test of proportions.

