8 STUDY DESIGN

8.1 Overview

The ETC-2015-002 study is a prospective, randomized, multicenter, pivotal clinical investigation. A total of 450 subjects will be enrolled across a maximum of 25 investigational sites. Fifty subjects (one per enrolling investigator) will be treated as roll-in patients; data from the roll-in subjects will only be considered for the safety analyses.

The estimated duration of the study is approximately 10 months from the time of first subject enrollment to the last study protocol-required follow-up visit. Each subject will be followed for 6 ± 2 weeks.

All patients presenting to the Investigator for elective (non-emergent) open cardiothoracic, abdominal, or orthopedic lower extremity surgical procedures are potential study subjects and should be screened for eligibility. Subjects will need to meet all eligibility in order to be enrolled into the investigation.

A subject is enrolled when he/she meets all preoperative inclusion/exclusion criteria, signs the informed consent forms, and meets the intraoperative inclusion criteria. The point of enrollment into the clinical investigation will occur intraoperatively.

Table 1 details the clinical investigation visits, corresponding timing, and evaluations to be performed at the visit. Table 2 lists the CRFs that need to be completed at each visit. Figure 1 represents the subjects' participation in the clinical investigation.

Table 1. Investigational Evaluation Schedule

Visit	Timing	Evaluations
Preoperative	Within 4 weeks before surgery	Informed consent, preoperative eligibility criteria confirmation, preoperative evaluations, and blood draw for antibody evaluation
Intraoperative	Day of surgery; day 0	Intraoperative inclusion criteria confirmation, efficacy assessments, and safety assessments
Postoperative	Postoperative day 1	Safety assessments
6 Week Follow-Up	6 weeks (± 2 weeks) postoperatively	Safety assessments, blood draw for antibody evaluation, and study discontinuation

[figure not shown]
Table 2. CRF Completion Schedule

CRF	Screening	Preoperative	Intraoperative	Postoperative	Follow-Up	Discontinuation
Preoperative Eligibility CRF	X					
Preoperative CRF		X				
Intraoperative CRF			X			
Concomitant Medication CRF		O	O	O	O	

Laboratory CRF		X		X		
Postoperative CRF				X		
Follow-Up CRF					X	
Discontinuation CRF						X
Adverse Event CRF			O	O	O	
Device Deficiency CRF			O			
Reoperation CRF				O	O	

X	Mandatory
O	As applicable

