10.6 Analysis of Safety

10.6.1 Analysis Population

Safety analyses will be conducted on the Full Analysis Population, defined as all subjects who were randomized into the study and received study intervention and all lead-in subjects.

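### Between-arm safety comparisons include up to 50 non-randomised lead-in subjects, all on HEMOBLAST

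*Protocol*

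**What the plan says.** Protocol 12.2.1 and 12.3.2.1 define the safety population as "all subjects who were randomized into the study and received study intervention and all lead-in subjects". SAP 10.2 and 10.6.1 repeat the definition. Protocol 12.2.1 and SAP 10.2 also group data summaries by the intervention received.

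Protocol 6.4.2 explains who the lead-ins are: "The first subject for each investigator will be treated as a lead-in subject". They are not randomised, and there are at most 50. Protocol 6.4.1 gives all of them HEMOBLAST. For randomised subjects both products are made ready at the start of surgery, whereas "all lead-in subjects will have a single HEMOBLAST™ device prepared". SAP 8.1 restricts their use: "data from the roll-in subjects will only be considered for the safety analyses".

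The safety analyses are comparative. Protocol 12.3.2.2 and SAP 10.6.2 state: "Comparisons of the proportion of subjects experiencing SAEs will be made between treatment arms". The same sections estimate arm differences in blood loss, intraoperative transfusion, operative time and hospital stay by linear regression. Reoperation and bleeding complications are compared by a general linear model. These models adjust for surgery type only, and no adjustment is stated for the SAE comparison.

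Neither document plans a safety comparison restricted to randomised subjects, a separate display of lead-ins, or a lead-in term in a model. The stratified displays in Protocol 12.2.3 and SAP 10.9 cover surgery type, number of applications, baseline SBSS score and coagulation status.

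**The concern.** Lead-ins differ from the randomised HEMOBLAST subjects in how they enter the trial, and the G+T group has no counterpart to them. Three features could matter:

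- Each is the investigator's first study subject, so a learning effect would count against HEMOBLAST.
- The investigator knows this subject will receive HEMOBLAST, so an easier first case could be chosen, which would favour HEMOBLAST.
- Treatment is known before the target bleeding site is picked. For randomised subjects the site is identified and scored before randomisation.

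The direction of any bias is therefore open, and adjustment for surgery type removes none of these effects. A contrast between HEMOBLAST with lead-ins and G+T without them loses the protection of randomisation, and no planned output would show whether lead-ins behaved differently.

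At stake are the comparative safety results of a pivotal trial whose stated objective (Protocol 5.1.1, SAP 6) is safety and efficacy relative to G+T.

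**Working it through.** **Inputs from the documents.** Randomised 267 HEMOBLAST and 133 G+T (Protocol 6.4.2); 160 and 80 at the interim (Table 9); re-estimated maximum of 460 (Protocol 12.4.3), taken as 307 and 153 under 2:1; lead-ins at most 50.

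**The plan's own figures.** 267 + 133 + 50 = 450, the stated maximum Full Analysis Population. Protocol 12.4.1 expects about 70 HEMOBLAST safety subjects per surgery type at an interim stop, counting the randomised subjects "plus up to an additional 50 lead-in subjects": (160 + 50)/3 = 70. Without lead-ins it would be 160/3 = 53. The plan's safety count therefore pools the two groups.

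**Lead-in share of the HEMOBLAST safety group**, w = L/(h + L), with L = 50:

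| Randomised | w | HEMOBLAST : G+T |
|---|---|---|
| 400 | 50/317 = 15.8% | 317/133 = 2.38 |
| 460 | 50/357 = 14.0% | 357/153 = 2.33 |
| 240 (interim stop) | 50/210 = 23.8% | 210/80 = 2.625 |

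With 25 lead-ins the shares are 8.6%, 7.5% and 13.5%. Because enrolment continues during the interim analysis, the share at an early stop would be somewhat below the 240-subject figure.

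**Shift in the arm difference.** Bias = w × (lead-in rate − randomised HEMOBLAST rate). The documents give no event rates, so these are assumptions: 20% in both randomised groups (no true device difference), lead-ins between 10% and 40%.

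- 400 randomised: 0.1577 × (−10 to +20) = −1.6 to +3.2 points.
- 240 randomised: 0.2381 × (−10 to +20) = −2.4 to +4.8 points.

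**Rejection rate of a nominal two-sided 5% z-test.** With bias b, the unpooled standard error SE_e that the analyst would compute, and the true sampling standard error SE_t:

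P(reject) = Φ((−1.96·SE_e − b)/SE_t) + 1 − Φ((1.96·SE_e − b)/SE_t)

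Example: 317 v 133, lead-ins at 40%.

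- b = 3.15 points; pooled HEMOBLAST rate = 23.15%.
- SE_e = √(0.2315 × 0.7685/317 + 0.16/133) = 4.20 points.
- SE_t = √((267 × 0.16 + 50 × 0.24)/317² + 0.16/133) = 4.18 points.
- The upper tail beyond (8.23 − 3.15)/4.18 = 1.22 is about 11.2%. The lower tail adds about 0.3%, giving about 11.5%.

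| Lead-in rate | 400 randomised, 50 lead-ins | 240 randomised, 50 lead-ins | 400 randomised, 25 lead-ins |
|---|---|---|---|
| 10% | 6.7% | 7.4% | 5.5% |
| 20% (equal) | 5.0% | 5.0% | 5.0% |
| 30% | 6.6% | 7.3% | 5.5% |
| 40% | 11.5% | 14.2% | 6.8% |

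**Precision lost by excluding lead-ins** (20% rate throughout):

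- Full size: √(0.16/317 + 0.16/133) = 4.13 points becomes √(0.16/267 + 0.16/133) = 4.25, a ratio of 1.027.
- Interim stop: √(0.16/210 + 0.16/80) = 5.26 points becomes √(0.16/160 + 0.16/80) = 5.48, a ratio of 1.042.

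**The case against.** **Pooling is inferred.** No sentence says that lead-ins enter the HEMOBLAST side of the tests. The SAE comparison refers to treatment arms, a term that Protocol 12.2.6 uses for randomised groups, and the figure of 70 per surgery type describes exposure. This does not carry the day. All safety analyses are assigned to the Full Analysis Population and summaries follow the treatment received, so pooling is the natural reading. If it was not intended, the text still needs correcting.

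**The larger figures are a ceiling.** Fifty is a maximum, and a 40% lead-in rate is double the assumed base rate, which nothing in the documents supports. With 25 lead-ins, or with 50 and a 5-point gap (5.4% at full size), the effect on the rejection rate is slight. This stands: the 11.5% and 14.2% figures are extreme cases.

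**The consequence is limited.** There is no safety hypothesis or success criterion, and under Protocol 12.2.4 "any comparisons that are not presented in the a priori specified testing procedure will also be considered exploratory". Investigators are trained before enrolling, and a Clinical Events Committee adjudicates SAEs for relatedness and expectedness. This stands as a limit on severity, but none of it makes the comparison randomised.

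**Every exposed subject belongs in the safety data.** Agreed. The dispute is only over which subjects feed the contrast.

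**Conclusion.** The concern holds. As written, the between-arm safety comparisons are partly non-randomised, with at most 15.8% of the HEMOBLAST group made up of lead-ins at the planned size and 23.8% at a stop with 240 randomised. The share is largest when randomised safety data are fewest.

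The documents do not show that bias exists, and its direction cannot be predicted. With 50 lead-ins and a 20% base rate, a 10-point gap either way moves the difference by 1.6 points at full size or 2.4 points at an interim stop. That raises a nominal 5% rejection rate to about 7%. Larger effects need a much larger gap.

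The primary non-inferiority result, its power and its type I error are untouched. The change should be made because the problem is avoidable at little cost, although it does not threaten the trial's main conclusion.

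**What to change.** In Protocol 12.2.1 and 12.3.2 and SAP 10.2 and 10.6:

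- Base every between-arm safety comparison on subjects who were randomised and treated.
- Show lead-ins in a separate column of the safety tables.
- Use the pooled HEMOBLAST group (randomised plus lead-in) only for single-arm AE, SAE, SADE and UADE rates with confidence intervals.
- Name the same randomised population for the exploratory comparisons in Protocol 5.4 and SAP 10.8. Those sections state none, and their outcomes overlap with the safety outcomes.

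The cost is wording, one table column and the wider standard errors shown above. At an interim stop the comparison would rest on about 53 HEMOBLAST subjects per surgery type in place of about 70. No exposure data are lost, and the efficacy sample size does not change.
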